7.11.1. Correlatives/Special Studies

Correlative Samples - Details for Lab Manual				
Correlative study (sample type)	Tissue CCR5 Staining*	Tissue PD-L1 Staining**	CTC PD-L1/ CCR5	CTC, CAMLs
Mandatory or Optional	Mandatory	Mandatory	Mandatory	Mandatory
Timing (+/- windows)	Archival or fresh	Archival or fresh	1-3 days	1-3 days
Volume Needed (blood only)	N/A	N/A	16 cc whole blood	20 cc whole blood for CTC and CAMLs
Tube type needed (blood only)	N/A	N/A	CellSave tube to be filled up completely.	CellSave tube to be filled up completely
Tissue thickness and/or # slides (tissue only)	5µ (No. of slides- TBD)	5µ (No. of slides- TBD)	N/A	N/A
Processing center (e.g. PCF- CTU)	PCF	TBD	CTCs Lab-NU	Creatv MicroTech, Inc

Correlative Samples - Details for Lab Manual				
Correlative study (sample type)	Tissue CCR5 Staining*	Tissue PD-L1 Staining**	CTC PD-L1/ CCR5	CTC, CAMLs
Sampling/ processing instructions	See lab manual	See lab manual	See lab manual	See lab manual
Shipping/delivery info	Medical College of Wisconsin (see below)	Reference laboratory	CTCs Lab-NU	Creatv MicroTech, Inc
Storage needs	Paraffin slides	Paraffin slides	See lab manual	See lab manual
Analysis center	See lab manual	See lab manual	CTC Lab-NU	See lab manual
Assay methodology	IHC	IHC	See below	See below

* Archival breast tissue (primary or metastatic site) will be collected from all patients at the pre-screening period and analyzed for presence of CCR5. Note: If no archival tissue is available, fresh core or excisional biopsy to be done of the primary or metastatic site.

** Breast tissue (primary or metastatic site) collected to analyze for the presence of CCR5 will additionally be used for evaluating PD-L1 expression levels. The PD-L1 expression testing will be performed at the reference laboratory using the formalin-fixed, paraffin-embedded (FFPE) tissue block or slides.

7.11.1.1 Sample Collection Guidelines

Please refer to laboratory manual for more details

7.11.1.3 Assay Methodology

CTCs Enumeration and PD-L1

CTC isolation and enumeration will be performed using the US Food and Drug Administration-approved CellSearch™ technology (Janssen Diagnostics). This technology consists of a semi-automated system for the preparation of a sample [Al-Kateb, 2015] and is used with the CellSearch™ Epithelial Cell Kit. The procedure enriches the sample for cells expressing the epithelial-cell adhesion molecule with antibody-coated magnetic beads, and labels the cells with the fluorescent nucleic acid dye 4,2-diamidino-2-phenylindole dihydrochloride (DAPI). Fluorescently labeled monoclonal antibodies specific for leukocytes (CD45-allophycocyanin) and epithelial cells (cytokeratin 8, 18, 19-phycoerythrin) are used to distinguish epithelial cells from leukocytes. A PD-L1 expression kit has been developed and is currently tested in clinical trial evaluating PD-L1 or PD-1 therapeutic targeting antibodies.

CTCs and CAMLs using CellSieve™

The CellSieve Microfiltration assay isolates CTCs and CAMLs by size exclusion, identifying CTCs or CAMLs by their morphological features and the phenotypic expression of CD14, cytokeratins 8, 18, and 19, CD45 and DAPI. The low-pressure vacuum system uses a specialized, holder attached to a syringe pump, to provide steady state flow of samples. Peripheral blood (7.5 mL) collected in CellSave preservative tubes is prefixed for 15 min, placed into the 30-mL syringe, and drawn through the filter in ~3 min. The filter is then washed, postfixed, and permeabilized for 15 min. The filter and cells are stained with an antibody mixture and blocking buffer of FITC-conjugated anti-cytokeratin 8, 18, 19, phycoerythrin (PE)-conjugated CD14, and Cy5-conjugated CD45 (Creatv MicroTech, Inc.).

CTCs are CD45/CD14 negative cells with a pleomorphic nucleus and a filamentous cytokeratin positive phenotype. CAMLs are morphologically identified as single cells with an enlarged nuclear profile (14–64 µm in diameter) or separated polymorphic nuclei contained within the cell. In addition, the nuclei had to be surrounded by a larger CD14 signal (21–300 µm in length). CAMLs can be identified further by vacuoles containing DAPI+ and/or cytokeratin.

7.12 STUDY TREATMENT APPLICATION

Refer to [Section 6.1](#) and [6.2](#) for details.

7.13 POST-INJECTION EVALUATION AND INJECTION SITE REACTION ASSESSMENT

At each treatment visit, an injection site reaction assessment will be made for the current and previous injection sites. Injection site reaction assessments are recorded by the Investigator starting after the first injection is given. Subject will be observed at approximately 30 minutes post-injection

[figure not shown]
or longer if necessary for injection site reaction as per CTCAE v5.0. Refer to [Sections 9.2.6](#) for more details.

7.14 PAIN ASSESSMENT USING VISUAL ANALOG SCALE (VAS)

Tolerability of repeated subcutaneous administration of leronlimab (PRO 140) is evaluated based on assessment of subject-perceived injection site pain using the Pain Visual Analog Scale (VAS). This assessment will be performed each time subjects arrive to the clinic for the study treatment visit.

Before and immediately after each study treatment administration, subjects will be asked to mark the point that best represents the pain intensity **over the past week** at the time of injection administration on a horizontal line (100 mm in length) anchored by the following word descriptors at each end, "no pain" on the left side and "pain as bad as it could possibly be" on the right side of the line. The subject marks on the line or by pointing to a position on the line the point that they feel represents their perception of their pain state. The VAS score is determined by measuring in millimeters from the left-hand end of the line to the point that the patient marks.

Figure 7-1: Visual Analog Scale

7.15 TUMOR IMAGING AND RESPONSE EVALUATION

For the purposes of this study, patients should be re-evaluated for response every 6 weeks for the first 13 months of treatment, and every 9 weeks thereafter. In addition to a baseline scan, confirmatory scans should also be obtained 6 weeks following initial documentation of objective response greater than Stable Disease (SD).

Response and progression will be evaluated in this study using the new international criteria proposed by the revised Response Evaluation Criteria in Solid Tumors (RECIST) guideline (version 1.1). Changes in the largest diameter (unidimensional measurement) of the tumor lesions and the shortest diameter in the case of malignant lymph nodes are used in the RECIST criteria.

High resolution CT with oral/intravenous contrast or contrast-enhanced MRI is the preferred imaging modalities for assessing radiographic tumor response. If a subject has a known allergy to

contrast material, please use local prophylaxis standards to obtain the assessment with contrast if at all possible, or use the alternate modality. In cases where contrast is strictly contraindicated, a non-contrast scan will suffice. Screening assessments should be performed within 28 days of registration. Brain MRI is the preferred imaging method for evaluating CNS metastasis, and assessment is required during screening in all eligible subjects. All known or suspected sites of disease (including CNS if history of CNS metastases) should be assessed at screening and at subsequent assessments using the same imaging method and technique. If more than one method is used at screening, then the most accurate method according to RECIST v1.1 should be used when recording data, and should again be used for all subsequent assessments. Previously treated CNS metastases are not considered measurable lesions for purposes of RECIST determined response. Subjects with a history of brain metastasis should have surveillance MRI approximately every 12 weeks, or sooner if clinically indicated.

Radiographic tumor assessments will be conducted at the end of 2 cycles (i.e., every 6 weeks) for the first 6 cycles (18 weeks) and at end of 3 cycles (i.e., every 9 weeks) thereafter, and at End of Treatment (EOT) visit by CT or MRI (per treating investigator's discretion); the same modality used at baseline should be used throughout. Tumor measurements will be done using RECIST v1.1. Tumor assessments for all subjects should continue as per protocol even if dosing is interrupted. Tumor measurements should be made by the same investigator or radiologist for each assessment whenever possible. Changes in tumor measurements and tumor responses to guide ongoing study treatment decisions will be assessed by the investigator using RECIST.

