3 STUDY DESIGN

This is a Phase Ib/II, multicenter study with a planned enrollment of up to 18 subjects in the Phase Ib portion of the study and 30 subjects in the Phase II portion of the study. The target population for this study is subjects with histologically confirmed diagnosis of CCR5 positive, metastatic triple-negative breast cancer (documented as having HER-2 negative, ER<1%, PR<1% disease) who are naïve to chemotherapy in metastatic setting (first-line) OR have failed first-line combination of chemotherapy and checkpoint inhibitor in metastatic setting (excluding carboplatin). A study flow schematic is presented in [Figure 3-1](#).

Figure 3-1: Study Schematic

Note: 1 treatment cycle = 21 (± 3) days

Note: Scans to be done at the end of 2 cycles (prior to Cycle 3) for the first 12 months and at the end of every 3 cycles (9 weeks) thereafter and at EOT, by CT, PET/CT, or MRI with contrast.

Phase Ib

Phase Ib is a dose escalation phase with 3 dose levels (cohorts) of leronlimab (PRO 140) administered in combination with a fixed dose of carboplatin at AUC 5. This dose finding portion of study will follow a “3+3” designed to determine the maximum tolerated dose (MTD) of leronlimab (PRO 140) administered as subcutaneous injection in subjects with histologically confirmed mTNBC that express CCR5. The MTD is defined as 1 dose level (cohort) below the dose in which dose limiting toxicities (DLTs) were observed in $\geq 33\%$ of the participants.

[figure not shown]
The calculation of the sample size for the Phase Ib trial is based on the traditional 3 + 3 dose escalation scheme which is conducted as follows:

- Subjects are treated in cohorts of three each receiving the same dose. For the assessment of a DLT subjects are observed for 3 weeks (Cycle 1) after the first application of the study treatment.
- If none of the three subjects of a cohort exhibits a DLT, the next cohort of three subjects receives the next higher dose.
- Otherwise, if at least one subject of a cohort exhibits a DLT, a further cohort of three subjects is treated at the same dose level (cohort) without escalating the dose.
- If exactly one out of the six subjects treated at this dose exhibits a DLT, the trial continues as planned at the next higher dose level (cohort).

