[8] Scans are to be done at the end of 2 cycles (i.e., every 6 weeks; [1-3 days before next cycle begins]) for the first 6 cycles (18 weeks) and at end of 3 cycles (i.e., every 9 weeks; [1-3 days before next cycle begins]) thereafter, and at End of Treatment (EOT) visit by CT, PET/CT or MRI with contrast (per treating investigator's discretion) using the same method as at baseline. Tumor measurements will be done using RECIST v1.1. To be assigned a status of PR or CR, changes in tumor measurements must be confirmed by repeat assessments that should be performed 6 weeks after the criteria for response are first met. In the case of SD, measurements must have met the SD criteria at least once after study entry at a minimum interval of 6 weeks.

[9] Hemoglobin, Hematocrit (HCT), Red Blood Cells (RBC), White Blood Cells (WBC) with total and differential count, absolute lymphocyte count, absolute neutrophil count (ANC) and platelets.

[10] Serum Biochemistry will include:
Hepatic function indicators: total bilirubin, direct bilirubin, alkaline phosphatase, aspartate aminotransferase (AST)/SGOT, alanine aminotransferase (ALT)/SGPT, albumin and total protein.
Renal function indicators: blood urea nitrogen (BUN), creatinine
Electrolytes: sodium, potassium, chloride, calcium and bicarbonate
Other: glucose (random)

[11] Urine samples will be tested for pH, appearance, color, specific gravity, turbidity, ketones, bilirubin, blood, glucose, protein, nitrites, urobilinogen, and leukocyte esterases. Microscopic exam includes bacteria, cast, crystals, epithelial cells, RBC and WBC.

[12] Only performed on women of childbearing potential

[13] Blood sample collection for CTCs PD-L1/CCR5 analysis to be taken prior to the treatment administration at baseline (C1D1), on Day 1 (CXD1) of each subsequent cycle, and at the end of treatment (EOT).

[14] Blood sample collection for CTC and CAMLs analysis to be taken prior to treatment administration at baseline (C1D1), on Day 1 (CXD1) of each subsequent cycle, and at the end of treatment (EOT).

[15] Archival breast tissue (primary or metastatic site) will be collected from all patients at the pre-screening period and analyzed for presence of CCR5. Note: If no archival tissue is available, fresh biopsy to be done of the primary or metastatic site.

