[16] Breast tissue (primary or metastatic site) collected to analyze for the presence of CCR5 will additionally be used for evaluating PD-L1 expression levels. The PD-L1 expression testing will be performed at the reference laboratory using the formalin-fixed, paraffin-embedded (FFPE) tissue block or slides.

[17] Leronlimab (PRO 140) is administered as subcutaneous injection in the abdomen weekly. A total of 350mg or 525 mg or 700mg (175 mg/mL) is delivered as two injections on opposite sides of the abdomen. The 350mg dose will be delivered as two injections of 1 mL each, 525mg dose will be delivered as two injections of 1.5 mL each and 700mg dose will be delivered as two injections of 2 mL each.

[18] Carboplatin will be IV infused at AUC 5 on D1 of each cycle, every 3 weeks

- [19] Injection Site Reaction Assessment as assessed by Investigator (or designee) at the clinic visits. Injection Site Reaction Assessment will not be applicable if leronlimab (PRO 140) is self-administered by subjects at home.
- [20] Subject-perceived injection site pain (average pain since last treatment) will be assessed using the Pain Visual Analog Scale (VAS) prior to each study treatment administration which evaluates average pain since last treatment. Injection Site Pain Assessment will not be applicable if leronlimab (PRO 140) is self-administered by subjects at home.
- [21] Subjects will be followed up by clinic visits or phone call or another method of contact, for survival status every 3 months (± 1 month) for 2 years after treatment discontinuation or until death, whichever occurs first
- [22] All subjects will be followed for adverse events for 30 days after last dose of leronlimab (PRO 140) and carboplatin, or until the subject starts a new treatment, whichever occurs first.
- [23] Subjects who discontinue treatment for unacceptable adverse event(s) will be followed until resolution or stabilization of the adverse event (i.e. the grade is not changing). If a subject stops treatment due to unacceptable adverse event(s) but has not demonstrated disease progression, then the subject will be followed with imaging studies every 9 weeks until the time of progression radiographically according to RECIST v1.1 criteria. In the event that a radiographic response is detected, then this event will be included as a response in the final analysis, and the time of progression used in calculation of the survival analysis.
- [24] Limited to all subsequent anti-cancer treatments.

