8.2 Analysis Primary Outcome Measure

8.2.1 Maximum Tolerated Dose (MTD) by evaluation of dose-limiting toxicities (DLTs) of leronlimab (PRO 140) when combined with carboplatin AUC5

The MTD will be summarized descriptively. The proportion of subjects at the different MTD levels and those who were able to tolerate the highest dose of leronlimab will be summarized descriptively.

8.2.2 Progression free survival (PFS) defined as time in months from the date of first study treatment to the date of disease progression or death from any cause, whichever comes first.

PFS will be calculated from the date of initial dose to the date of objective disease progression or death due to any cause, whichever occurs earlier. If patients discontinued treatment due to toxicity, withdrew consent without disease progression or death, PFS will be censored at the date of the last evaluable tumor assessment. A patient with no evaluable tumor assessments or who drop out before first follow-up period will be censored at the date of informed consent. If two or more consecutively scheduled tumor assessments have no data (not evaluable due to incomplete assessment, not assessed, or missing) and are followed by a PD assessment or death, the PFS will be censored at the last evaluable tumor assessment date prior to the assessments with no data. Patients will be explicitly censored for PFS at last adequate tumor assessment prior to initiation of new anticancer treatment or radiation.

Patients who are off-treatment without objective PD and getting the subsequent new anticancer therapy before the data cut-off then PFS will be censored at the last adequate tumor assessment before the new anticancer treatment start, regardless of whether there was a PD or death after the start of the new anticancer treatment.

Progression free survival (PFS) will be estimated using Kaplan-Meier curves, and the median PFS will be read from this curve.

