Carboplatin administration [17]			Х			X			X				
Post Injection Site Evaluation by Investigator [18]			Х	Х	Х	Х	Х	Х	Х	X	Х		
Injection Site Pain Assessment (VAS) [19]				X	X	X	X	X	X	X	X		
Survival status												X	X[20]
Concomitant medications	Х	Х	Х	Х	Х	Х	Х	Х	Х	Х	Х	Х	X[23]
Adverse Events			Х	Х	Х	X	Х	Х	X	Х	Х	Х	

Footnotes

- [1] A separate Informed Consent Form (ICF) will be used for the pre-screening. The pre-screening period is designed for evaluation of histologically confirmed diagnosis of TN MBC (documented by HER-2 negative, ER<1%, PR<1%) and CCR5 positive status by Immunohistochemistry (IHC) assay. This assay will be performed in archival tissue from previous biopsy specimens. If archival tissue is not available then, fresh core or excisional biopsy will be done. If patient qualifies, then they will undergo full screening.
- [2] Informed consent must be obtained prior to patient participation in any protocol-related activities that are not part of routine care.
- [3] A complete review of the subject's past medical history, past surgeries, and current therapies (medications and non-medications) will be undertaken by the Investigator to check that all inclusion and no exclusion criteria have been met.
- [4] Vital signs include blood pressure, heart rate, respiration rate, and temperature.
- [5] Weight only
- [6] Symptom-directed physical examination

- [7] A 12-lead EKG will be repeated during the study only if clinically indicated and at the discretion of the treating physician.
- [8] Scans are to be done at the end of 2 cycles (prior to cycle 3) for the first 13 months and at end of 3 cycles (9 weeks) thereafter, and at End of Treatment (EOT) visit by CT, PET/CT or MRI with contrast (per treating investigator's discretion) using the same method as at baseline. Tumor measurements will be done using RECIST1.1. To be assigned a status of PR or CR, changes in tumor measurements must be confirmed by repeat assessments that should be performed 6 weeks after the criteria for response are first met. In the case of SD, measurements must have met the SD criteria at least once after study entry at a minimum interval of 6 weeks.
- [9] Hemoglobin, Hematocrit (HCT), Red Blood Cells (RBC), White Blood Cells (WBC) with total and differential count, absolute lymphocyte count, absolute neutrophil count (ANC) and platelets.
- [10] Serum Biochemistry will include:

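### The scan calendar that dates progression for primary PFS is stated in three conflicting lengths, and SAP 8.2.2 does not say which one its missed-assessment censoring rule counts against

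*Protocol*

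**What the plan says.** Twelve places in current text give the length of the 6-weekly scanning phase, after which scans are 9-weekly.

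- **18 weeks (nine places).** Protocol: Synopsis (Trial Design and Secondary Outcome Measures), Section 3 (Phase II text), Table 4-1 footnote 8, the later part of 7.15, and 8.7.3.1. SAP: 2.1, 2.4.2 and 8.3.2. Protocol 7.15 puts it as "at the end of 2 cycles (i.e., every 6 weeks) for the first 6 cycles (18 weeks) and at end of 3 cycles".
- **12 months (one place).** Protocol Section 3, note to Figure 3-1: "Scans to be done at the end of 2 cycles (prior to Cycle 3) for the first 12 months".
- **13 months (two places).** The opening of Protocol 7.15: "patients should be re-evaluated for response every 6 weeks for the first 13 months of treatment, and every 9 weeks thereafter". SAP Appendix 1, footnote 8: "Scans are to be done at the end of 2 cycles (prior to cycle 3) for the first 13 months".

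The primary Phase II endpoint is PFS, estimated by Kaplan-Meier; SAP 8.2.2 says "the median PFS will be read from this curve". The same section has a missed-scan rule that begins "If two or more consecutively scheduled tumor assessments have no data (not evaluable due to incomplete assessment, not assessed, or missing". If progression or death follows such a gap, PFS is censored at the last evaluable assessment before it. The rule gives no cross-reference to a schedule, no window and no gap in weeks.

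For patients who stop because of toxicity without progression, Protocol Table 4-1 footnote 23, 4.4 and 4.4.2 say "then the subject will be followed with imaging studies every 9 weeks until the time of progression radiographically", and that the progression time enters the survival analysis. SAP Appendix 1 footnote 22 repeats this.

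**The concern.** Progression seen on imaging is dated at a scan, so the calendar is part of the definition of the primary endpoint. Protocol 7.15 contradicts itself, and so does the SAP, so neither document settles the question alone.

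Two things follow. If sites follow different passages, the same tumour growth can be dated 3 or 6 weeks apart. And even with the scan history fixed, the missed-assessment rule cannot be programmed without choosing a calendar, and that choice can turn an event into a censored time. In an open-label trial the choice would be made with outcomes visible. SAP 7.4 plans no sensitivity analysis that would show how much depends on it.

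**Working it through.** **Inputs.** The cycle is 21 days (Protocol Section 4), so 6 cycles = 126 days = 18 weeks, as the documents state. The reference PFS is about 5 months (Protocol Section 3; SAP 2.1). Phase II has 30 patients, chosen by clinical judgment (SAP 3), so there is no power figure to reproduce. One month is taken as 4.348 weeks, so 5 months = 21.74, 12 months = 52.2 and 13 months = 56.5 weeks.

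**Scan weeks.**

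| Calendar | Scan weeks |
|---|---|
| 18 weeks | 6, 12, 18, 27, 36, 45, 54, 63, 72 |
| 12 months, 9-weekly counted from the week 48 scan | 6, 12, 18, 24, 30, 36, 42, 48, 57, 66, 75 |
| 12 months, 9-weekly counted by cycle number | 6, 12, 18, 24, 30, 36, 42, 48, 54, 63, 72 |
| 13 months | 6, 12, 18, 24, 30, 36, 42, 48, 54, 63, 72 |

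The Figure 3-1 note allows either reading of the 12-month calendar. All calendars agree to week 18.

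**Censoring rule, same scan history.**

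| Last scan / progression found | Missed, 18-week calendar | Missed, 12- or 13-month calendar |
|---|---|---|
| Week 18 / week 36 | 27 (one): event at week 36 | 24, 30 (two): censored at week 18 |
| Week 36 / week 54 | 45 (one): event at week 54 | 42, 48 (two): censored at week 36 |

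Both reversals hold for any assessment window from 0 to 3 weeks.

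**Progression dates that differ.** Assume exponential PFS with median *m* weeks and every event dated at the next scan: S(t) = 2^(−t/m). Between weeks 18 and 54, the 18-week and 13-month calendars give different dates for progression in (18, 30] and (36, 48], and the same date in (30, 36] and (48, 54]. They coincide from week 54. With m = 21.74:

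- S(18) − S(30) = 0.563 − 0.384 = 0.179
- S(36) − S(48) = 0.317 − 0.216 = 0.101
- Total 0.280, or 28%. The 18-week calendar dates progression later in 21% and earlier in 7%.

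For true medians of 4, 5, 6 and 7 months the totals are 27.6%, 28.0%, 27.4% and 26.4%. If 10% or 20% of events are deaths (an assumption), the 5-month figure falls to about 25% or 22%.

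For 18 weeks against 12 months at a 5-month median, counting by cycle number gives the same 28%. Counting from week 48 makes every later date differ as well: 0.280 + S(48) = 0.280 + 0.216 = 0.496, about 50%.

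**Population median read-out.** This is the first scan on or after the true median.

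| True median | 18-week calendar | 12- or 13-month calendar |
|---|---|---|
| 4 months (17.4 weeks) | week 18 | week 18 |
| 5 months (21.7 weeks) | week 27 | week 24 |
| 6 months (26.1 weeks) | week 27 | week 30 |
| 7 months (30.4 weeks) | week 36 | week 36 |

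**One trial of 30.** In 100,000 simulated trials at a 5-month median, reading the 15th ordered time and comparing the 18-week with the 13-month calendar, the mean shift is about 0.31 months later on the 18-week calendar. The sampling SD is 1.34 to 1.48 months. The shift is zero in 36% of trials and reversed in 14%. For true medians of 4 to 7 months the mean shift is 0.20 to 0.34 months.

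**The case against.** The best defence is that the intended calendar is not hard to guess. Nine of twelve places say 18 weeks, including Protocol Table 4-1 and the body of the SAP, and SAP 1 describes itself as only a limited overview of the protocol. That is good evidence of intent. It is not a precedence rule, and deferring to the protocol does not help when Protocol 7.15 gives two answers.

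The effect on the median is also small beside sampling error, no formal test is planned (SAP 5), and confirmatory and end-of-treatment scans, which are not modelled here, would narrow some differences. All of that stands and limits the weight of the point.

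Several stronger readings are tempting, and the documents do not support them:

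- **Half of all progression dates are in doubt.** The 50% figure needs the 12-month calendar and 9-weekly counting from week 48. Counted by cycle number it is 28%.
- **The 18-week calendar always inflates the median.** The population read-out moves not at all, later, earlier and not at all at true medians of 4, 5, 6 and 7 months.
- **The calendar decides whether the median exceeds 5 months.** If the 15th ordered time is read, that chance is 69.9% on every calendar. A gap of 81.2% against 70.5% appears only if the 15th and 16th times are averaged with no censoring. With up to 1 to 3 of 30 patients censored by week 18 (an assumption) it shrinks to 77% v 73%, 76% v 74% and 76% v 75%. The SAP attaches no decision to 5 months.
- **Patients who stop for toxicity have no PFS rule.** SAP 8.2.2 does have one: it censors them at the last evaluable assessment. The open question is how that sentence fits with imaging continued to progression.

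**Conclusion.** The point holds as an internal inconsistency that reaches the primary endpoint, and it should be fixed. Three lengths for the 6-weekly phase stand in current text, each document contradicts itself, and SAP 8.2.2 censors on scheduled assessments without naming the schedule. Identical data (scans at weeks 18 and 36, or 36 and 54) give opposite event status on calendars the documents state. This part rests on no distributional assumption.

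The numerical size does rest on assumptions: exponential PFS, full scan adherence and scan-dated events. On those, about 28% of progression dates differ between the 18-week and 13-month calendars (26 to 28% for true medians of 4 to 7 months), and 28% to 50% between the 18-week and 12-month calendars at a 5-month median. The mean shift in one trial's median is about 0.31 months and its direction varies. The documents give no missed-scan rate, so the number of patients the censoring rule would reclassify is unknown. With one arm and no formal test, what is affected is the dating and censoring behind a descriptive estimate, not type I error or power.

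**What to change.** 1. Reconcile the twelve places listed above to one scanning schedule of the sponsor's choosing. No view is taken here on which interval is clinically right.
2. In SAP 8.2.2, state that *scheduled* means that schedule, and give the gap in weeks between evaluable scans that counts as two missed assessments.
3. Separately, reconcile the SAP 8.2.2 sentence that censors toxicity discontinuations at the last evaluable assessment with Protocol Table 4-1 footnote 23, 4.4 and 4.4.2 (and SAP Appendix 1 footnote 22), which continue 9-weekly imaging and use the resulting progression time. State whether progression found on that imaging is a PFS event.

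The cost is low: a protocol clarification, matching SAP text and a few sentences in 8.2.2, all before database lock and with no new data collection. Scans already taken under different readings cannot be re-dated, but a by-subject listing of actual scan weeks would show how many patients are affected.
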